## 9 DATA COLLECTION, RETENTION AND MONITORING

### 9.1 Data Collection and Management

Data will be collected on paper worksheets and entered into the Research Electronic Data Capture (REDCap) system by dedicated clinical research coordinators using study-specific clinical research forms. REDCap is an easy-to-use highly secure data management system provided by UCSF to investigators for research use at no charge. All REDCap data will be reviewed and cleaned by the study investigators after data entry. Paper worksheets will be kept in patient binders as backup and securely stored.

### 9.2 Availability and Retention of Investigational Records

The Investigator will make study data accessible to the IRB, and other interested parties upon request. A file for each subject must be maintained that includes the signed Informed Consent and copies of all source documentation related to that subject. The Investigator must ensure the reliability and availability of source documents from which the information on the CRF was derived. All study documents (patient files, signed informed consent forms, copies of CRFs, Study File Notebook, etc.) must be kept secured for a period of two years.

### 9.3 Subject Confidentiality

In order to maintain subject confidentiality, only a site number, subject number and subject initials will identify all study subjects on CRFs.

## 10 ADMINISTRATIVE, ETHICAL, REGULATORY CONSIDERATIONS

The study will be conducted according to the Declaration of Helsinki, Protection of Human Volunteers (21 CFR 50), Institutional Review Boards (21 CFR 56), and Obligations of Clinical Investigators (21 CFR 312).

To maintain confidentiality, all laboratory specimens, evaluation forms, reports and other records will be identified by a coded number and initials only. All study records will be kept in a locked file cabinet and code sheets linking a patient's name to a patient identification number will be stored separately in another locked file cabinet. Clinical information will not be released without written permission of the subject, except as legally required. The Investigator must also comply with all applicable privacy regulations (e.g., Health Insurance Portability and Accountability Act of 1996, EU Data Protection Directive 95/46/EC).

## 10.1 Protocol Amendments

Protocol amendments will not be implemented without prior written IRB approval except as necessary to eliminate immediate safety hazards to patients. A protocol amendment intended to eliminate an apparent immediate hazard to patients may be implemented immediately, provided the IRBs are notified within five working days.

## 10.2 Institutional Review Boards

The protocol and consent form will be reviewed and approved by the IRB at UCSF prior to study initiation. Serious adverse experiences will be reported to the IRB/IEC in accordance with the standard operating procedures and policies of the IRB, and the Investigator will keep the IRB informed as to the progress of the study. The Investigator will obtain assurance of IRB compliance with regulations.

Any documents that the IRB may need to fulfill its responsibilities (such as protocol, protocol amendments, consent forms, information concerning patient recruitment, payment or compensation procedures, or other pertinent information) will be submitted to the IRB. The IRBs written unconditional approval of the study protocol and the informed consent form will be in the possession of the Investigator before the study is initiated. This approval must refer to the study by exact protocol title and number and should identify the documents reviewed and the date of review.

Protocol and/or informed consent modifications or changes may not be initiated without prior written IRB approval except when necessary to eliminate immediate hazards to the patients or when the change(s) involves only logistical or administrative aspects of the study. Such modifications will be submitted to the IRB and written verification that the modification was submitted and subsequently approved should be obtained.

The IRB must be informed of revisions to other documents originally submitted for review; serious and/or unexpected adverse experiences occurring during the study in accordance with the standard operating procedures and policies of the IRB; new information that may affect adversely the safety of the patients of the conduct of the study; an annual update and/or request for re-approval; and when the study has been completed.

## 10.3 Informed Consent Form

Informed consent will be obtained in accordance with the Declaration of Helsinki, ICH GCP, US Code of Federal Regulations for Protection of Human Subjects (21 CFR 50.25[a,b], CFR 50.27, and CFR Part 56, Subpart A), the Health Insurance Portability and Accountability Act (HIPAA, if applicable), and local regulations.

The Investigator will prepare the informed consent form and HIPAA authorization prior to submission to the IRB/IEC. The written consent document will embody the elements of informed consent as described in the International Conference on Harmonisation and will also comply with local regulations. The Investigator will send an IRB-approved copy of the Informed Consent Form to the Sponsor (or designee) for the study file.

A properly executed, written, informed consent will be obtained from each subject prior to entering the subject into the trial. Information should be given in both oral and written form and subjects must be given ample opportunity to inquire about details of the study. If

appropriate and required by the local IRB, assent from the subject will also be obtained. A copy of the signed consent form will be given to the subject and the original will be maintained with the subject's records.

#### **10.4 Publications**

The preparation and submittal for publication of manuscripts containing the study results shall be in accordance with a process determined by the investigators. The publication or presentation of any study results shall comply with all applicable privacy laws, including, but not limited to, the Health Insurance Portability and Accountability Act of 1996.

A publication will be done at the end of the 52-week trial, and a separate publication will potentially be done at the end of the extension phase of trial.

#### **10.5 Investigator Responsibilities**

By signing the Agreement of Investigator form, the Investigator agrees to:

1. Conduct the study in accordance with the protocol and only make changes after notifying the Sponsor (or designee), except when to protect the safety, rights or welfare of subjects.
2. Personally conduct or supervise the study (or investigation).
3. Ensure that the requirements relating to obtaining informed consent and IRB review and approval meet federal guidelines, as stated in § 21 CFR, parts 50 and 56.
4. Ensure that all associates, colleagues and employees assisting in the conduct of the study are informed about their obligations in meeting the above commitments.
5. Maintain adequate and accurate records in accordance with §21 CFR 312.62 and to make those records available for inspection when required.
6. Ensure that an IRB that complies with the requirements of §21 CFR part 56 will be responsible for initial and continuing review and approval of the clinical study.
7. Promptly report to the IRB all changes in the research activity and all unanticipated problems involving risks to subjects or others.
8. Seek IRB approval before any changes are made in the research study, except when necessary to eliminate hazards to the patients/subjects.
9. Comply with all other requirements regarding the obligations of clinical investigators and all other pertinent requirements listed in § 21 CFR part 312.

## 11 SAFETY REPORTING OF ADVERSE EVENTS

### 11.1 Assessment of Safety

#### 11.1.1 Specification of Safety Variables

Safety assessments will consist of monitoring and reporting adverse events (AEs) and serious adverse events (SAEs) per protocol. This includes all events of death, and any study specific issue of concern.

#### 11.1.2 Adverse Events

An AE is any unfavorable and unintended sign, symptom, or disease temporally associated with the use of an investigational medicinal product (IMP) or other protocol-imposed intervention, regardless of attribution.

This includes the following:

- AEs not previously observed in the subject that emerge during the protocol-specified AE reporting period, including signs or symptoms associated with RCLAD that were not present prior to the AE reporting period.
- Complications that occur as a result of protocol-mandated interventions (e.g., invasive procedures such as cardiac catheterizations).
- If applicable, AEs that occur prior to assignment of study treatment associated with medication washout, no treatment run-in, or other protocol-mandated intervention.
- Preexisting medical conditions (other than the condition being studied) judged by the investigator to have worsened in severity or frequency or changed in character during the protocol-specified AE reporting period.

#### 11.1.3 Serious Adverse Events

An AE should be classified as an SAE if the following criteria are met:

- It results in death (i.e., the AE actually causes or leads to death).
- It is life threatening (i.e., the AE, in the view of the investigator, places the subject at immediate risk of death. It does not include an AE that, had it occurred in a more severe form, might have caused death.).
- It requires or prolongs inpatient hospitalization.
- It results in persistent or significant disability/incapacity (i.e., the AE results in substantial disruption of the subject's ability to conduct normal life functions).
- It results in a congenital anomaly/birth defect in a neonate/infant born to a mother exposed to the IMP.
- It is considered a significant medical event by the investigator based on medical judgment (e.g., may jeopardize the subject or may require medical/surgical intervention to prevent one of the outcomes listed above).

## **11.2 Methods and Timing for Assessing AND Recording Safety variables**

The investigator is responsible for ensuring that all AEs and SAEs that are observed or reported during the study, are collected and reported to the FDA, appropriate IRB(s), and Genentech, Inc. in accordance with CFR 312.32 (IND Safety Reports).

### **11.2.1 Adverse Event Reporting Period**

The study period during which all AEs and SAEs must be reported begins after informed consent is obtained and initiation of study treatment and ends 28 days following the last administration of study treatment or study discontinuation/termination, whichever is earlier. After this period, investigators should only report SAEs that are attributed to prior study treatment.

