| DURATION OF SUBJECT PARTICIPATION AND DURATION OF STUDY | 
Subjects will be in the study for 56 weeks. Subjects that wish to continue taking pirfenidone beyond 56 weeks may be eligible for PIRCLAD extension until September 30, 2021. The Principal Investigator will determine eligibility for PIRCLAD extension on a case by case basis. Subjects must continue to meet the inclusion and exclusion criteria, and continue monitoring with laboratory tests, study coordinator calls, clinic visits, pulmonary function tests, and CT scan imaging.
 
The total duration of the study is expected to be up to 48 months. Fifteen months will be for subject recruitment and an additional 14 months for subject follow-up. Subjects eligible for PIRCLAD extension will have up to 19 months of follow up. The last study coordinator call will be 28 days after the last pirfenidone dose.
   |
| CONCOMITANT MEDICATIONS                                 | 
Patients will continue their current immunosuppression regimen consisting of prednisone, mofetil mycophenolate, tacrolimus and sirolimus.
 
Strong inhibitors of CYP1A2 (e.g. fluvoxamine or enoxacin) and moderate inhibitors of CYP1A2 (e. g. mexiletine, thiabendazole, or phenylpropanolamine) will not be allowed. Ciprofloxacin will be allowed only at doses equal or less than 500 mg twice daily.
  |

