## 6 STUDY PROCEDURES AND GUIDELINES

A Schedule of Events representing the required testing procedures to be performed for the duration of the study is diagrammed below.

| Week                   | 1 | 2 | 3 | 4 | 5 | 6 | 8 | 12 | 16 | 20 | 24 | 28 | 32 | 36 | 40 | 44 | 48 | 52 | 56 | 57 | 60 |
|------------------------|---|---|---|---|---|---|---|----|----|----|----|----|----|----|----|----|----|----|----|----|----|
| Start Pirfenidone      | x |   |   |   |   |   |   |    |    |    |    |    |    |    |    |    |    |    |    |    |    |
| Study coordinator call |   | x |   | x |   | x |   | x  | x  | x  | x  | x  | x  | x  | x  | x  | x  | x  | x  | x  |    |
| Tacrolimus level       | x | x | x | x | x | x | x | x  | x  | x  | x  | x  | x  | x  | x  | x  | x  | x  | x  | x  | x  |
| Liver function tests   |   |   |   | x |   |   | x | x  | x  | x  | x  |    |    | x  |    |    | x  |    |    |    |    |
| Clinic visit           |   |   |   |   |   |   | x |    |    | x  |    |    | x  |    |    | x  |    | x  |    |    |    |
| FVC measure            |   |   |   |   |   |   | x |    |    | x  |    |    | x  |    |    | x  |    | x  |    |    |    |
| CT scan                |   |   |   |   |   |   |   |    |    |    | x  |    |    |    |    |    |    |    |    |    |    |
| Stop Pirfenidone       |   |   |   |   |   |   |   |    |    |    |    |    |    |    |    |    |    |    |    | x  |    |

Prior to conducting any study-related activities, written informed consent must be signed and dated by the subject.

Any clinically significant findings will be communicated to the patients and, with their consent, to the patients' clinical providers.

**Study coordinator call:** Our study coordinator will contact subjects by phone every 2 weeks for the first 6 weeks to inquire about treatment-emergent adverse events (TEAE) and then monthly. TEAE will be recorded and graded according to the Common Terminology Criteria for Adverse Events (CTCAE) v3.0^21. The last phone call will be 28 days after the last pirfenidone dose. Subjects will be provided a phone number to report any additional TEAE. A Data Safety Monitoring Board will be convened.

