#### Protocol Amendment

Subjects that wish to continue taking pirfenidone beyond 56 weeks may be eligible for PIRCLAD extension for up to 76 weeks. The Principal Investigator will determine eligibility for PIRCLAD extension after reviewing the 52-week study coordinator call. Subjects must continue to meet the original inclusion and exclusion criteria. Subjects will continue to be monitored per study protocol (laboratory tests, study coordinator calls, clinic visits, pulmonary function tests, and CT scan imaging) as long as they remain on pirfenidone. The last pirfenidone dose will be on September 30, 2021. The last study coordinator call will occur 28 days after the last pirfenidone dose. Reporting of adverse events and protocol violations for these subjects will remain the same. The duration of PIRCLAD extension is diagrammed below.

| Week                   | 56 | 60 | 64 | 68 | 72 | 76 | 80 | 84 | 88 | 92 | 96 | 100 | 104 | 108 | 112 | 116 | 120 | 124 | 128 | 129 | 132 |
|------------------------|----|----|----|----|----|----|----|----|----|----|----|-----|-----|-----|-----|-----|-----|-----|-----|-----|-----|
| Continue Pirfenidone   | x  |    |    |    |    |    |    |    |    |    |    |     |     |     |     |     |     |     |     |     |     |
| Study coordinator call | x  | x  | x  | x  | x  | x  | x  | x  | x  | x  | x  | x   | x   | x   | x   | x   | x   | x   | x   | x   | x   |
| Tacrolimus level       | x  | x  | x  | x  | x  | x  | x  | x  | x  | x  | x  | x   | x   | x   | x   | x   | x   | x   | x   | x   | x   |
| Liver function tests   | x  |    |    | x  |    |    | x  |    |    | x  |    |     | x   |     |     | x   |     | x   |     | x   |     |
| Clinic visit           | x  |    |    | x  |    |    | x  |    |    | x  |    |     | x   |     |     | x   |     | x   |     | x   |     |
| FVC measure            | x  |    |    | x  |    |    | x  |    |    | x  |    |     | x   |     |     | x   |     | x   |     | x   |     |
| CT scan                |    |    |    |    |    |    |    |    |    |    |    |     | x   |     |     |     |     |     |     |     |     |
| Stop Pirfenidone       |    |    |    |    |    |    |    |    |    |    |    |     |     |     |     |     |     |     |     | x   |     |

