#### **11.3.2.6 e. Pregnancy**

If a female subject becomes pregnant while receiving the study drug or within 28 days after the last dose of study drug, or if the female partner of a male study subject becomes pregnant while the study subject is receiving the study drug or within 28 days after the last dose of study drug, a report should be completed and expeditiously submitted to Genentech, Inc. Follow-

up to obtain the outcome of the pregnancy should also occur. Abortion, whether accidental, therapeutic, or spontaneous, should always be classified as serious, and expeditiously reported as an SAE. Similarly, any congenital anomaly/birth defect in a child born to a female subject exposed to Pirfenidone should be reported as an SAE.

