#### ***11.3.2.7 f. Post-Study Adverse Events***

The investigator should expeditiously report any SAE occurring after a subject has completed or discontinued study participation if attributed to prior Pirfenidone exposure. If the investigator should become aware of the development of cancer or a congenital anomaly in a subsequently conceived offspring of a female subject who participated in the study, this should be reported as an SAE.

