## **WITHDRAWAL**

### **Discontinuation of Patients:**

The investigator will discontinue patients from the study drug or the study or both in the following circumstances:

- The patient, for any reason, requires treatment with another therapeutic agent that has been demonstrated to be effective for treatment of the study indication. In this case, discontinuation from the study occurs prior to introduction of the new agent.

- The investigator decides that the patient should be withdrawn from the study. If a serious adverse event or a clinically significant laboratory value is the basis for this decision, the investigator will discontinue the study therapy and take appropriate measures. The investigator must **immediately** notify the study sponsor or its designee.
- The patient or attending physician requests withdrawal of the patient from the study.
- The investigator or the study sponsor stops the study or stops the patient's participation in the study for medical, safety, regulatory, or other reasons consistent with applicable laws, regulations, and good clinical practice (GCP).
- The study therapies have shown unacceptable toxicity.
- The patient becomes pregnant or fails to use adequate birth control (for women with reproductive potential).
- The patient is noncompliant with study procedures.

When a subject withdraws before completing the study, the reason for withdrawal is to be documented in the CRF and in the source document.

Study agents assigned to the withdrawn subject may not be assigned to another subject. Subjects who withdraw will not be replaced.

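### As plainly read, section 11.2.1 ends adverse event reporting at study exit, so a subject who leaves within 28 days of the last dose loses some or all of the post-dose window that other sections assume

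*Combined protocol and SAP*

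**What the plan says.** Section 11.2.1 opens the reporting period after consent and the start of treatment. The period "ends 28 days following the last administration of study treatment or study discontinuation/termination, whichever is earlier". The next sentence limits what follows: "After this period, investigators should only report SAEs that are attributed to prior study treatment". Section 11.3.2.7 repeats that limit for subjects who have left: "The investigator should expeditiously report any SAE occurring after a subject has completed or discontinued study participation if attributed to prior Pirfenidone exposure".

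Three other places fix the last safety contact by the last dose alone. Section 6 says "The last phone call will be 28 days after the last pirfenidone dose". The synopsis says "The last study coordinator call will be 28 days after the last pirfenidone dose". The Protocol Amendment text for the extension says "The last study coordinator call will occur 28 days after the last pirfenidone dose". None makes an exception for a subject who leaves early. The pregnancy rule in section 11.3.2.6 likewise runs "within 28 days after the last dose of study drug" and is not cut at study exit.

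The Withdrawal section lets drug and study end together: "The investigator will discontinue patients from the study drug or the study or both in the following circumstances". The listed circumstances include unacceptable toxicity, a request by the patient or attending physician, and the need for another effective therapy.

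**The concern.** The primary objective is safety and tolerability in 10 subjects, so the post-dose record of each subject matters. If reporting closes at study exit, subjects withdrawn early are followed for less time after the last dose than those who complete, and some of them will be leaving because of toxicity.

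Once the period has closed, a non-serious AE that starts or worsens is no longer reportable. Nor is an SAE judged unrelated to pirfenidone. Section 11.3.2.2 asks for every death whatever its attribution, but only within this same period, so a death judged unrelated soon after an early exit could go unreported. The synopsis states that about 60% of patients with this disease die within a year, so such a death is plausible. Section 11.2.2 also asks for AE end dates, and section 11.2.3 counts improvement after stopping drug among its criteria for relatedness. Both draw on observation after the last dose.

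**Working it through.** No sample size or error rate is involved. The check is day arithmetic on the wording, followed by a comparison of sections.

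**Inputs.** Day 0 is the last dose. D is the day of study exit, with D ≥ 0, on the assumption that study drug is not given after a subject has left the study. The target window is 28 days (section 6, synopsis, Protocol Amendment).

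**Reading A:** the period ends at day 28 or at study exit, whichever comes first. End = min(28, D); days lost = 28 − min(28, D).

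**Reading B:** the period ends 28 days after the earlier of the last dose and study exit. End = 28 + min(0, D) = 28 for every D ≥ 0.

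| D (study exit) | End, reading A | Days lost, reading A | End, reading B |
|---|---|---|---|
| 0 | 0 | 28 | 28 |
| 1 | 1 | 27 | 28 |
| 7 | 7 | 21 | 28 |
| 14 | 14 | 14 | 28 |
| 28 | 28 | 0 | 28 |
| 29 | 28 | 0 | 28 |

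**Which reading the words support.** Under B, the last dose always comes first or ties, so the earlier-of qualifier never changes the answer. Only A gives it any effect. A is therefore the plain reading, although B is grammatical.

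**Who is affected under A.** Only subjects with D below 28: those taken off drug and study together, or leaving the study within 28 days of the last dose. A subject who stops drug but stays in the study loses nothing. Nor does a subject removed under the Discontinuation rule for more than 28 consecutive missed days, because D is then at least 29 and the window is already complete.

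**What is affected under A.**
- Lost: non-serious AEs, and SAEs and deaths not attributed to pirfenidone, between day D and day 28.
- Kept: SAEs attributed to pirfenidone, with no time limit stated (sections 11.2.1 and 11.3.2.7).
- Number discontinuing for a TEAE: unchanged, because it is fixed by the reason for stopping drug.
- Proportion with a TEAE: unchanged for anyone who left because of one. It could change only for a leaver with no earlier TEAE.

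**The case against.** The best defence is that reading B is grammatical and agrees with the three statements about the last call and with the pregnancy window, whereas reading A contradicts them. Redundant qualifiers are common in protocols. The call at day 28 is in any case required, section 6 makes coordinator calls the means of asking about TEAEs, and serious toxicity attributed to drug stays reportable. On this view the sentence is only clumsy.

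Most of this stands as a limit on the harm. It does not rescue the sentence. Staff applying section 11.2.1 must choose between two readings, and the one that gives every word a function closes the period early. A call made after the period has closed could turn up events that the section no longer asks anyone to report.

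Three stronger inferences are tempting, and the documents do not support them.
- A reader might infer that the proportion with a TEAE is selectively underestimated. A subject who leaves for toxicity is already counted in that proportion and in the primary count. The Stopping Rules section also cites AEs in 99% of pirfenidone patients in the earlier trials, which suggests the proportion has little room to move.
- A reader might infer that 3 of the 10 subjects would have no post-dose coverage. The Stopping Rules figure is an upper expectation for stopping the drug. Nothing says that those subjects also leave the study, still less on the same day.
- A reader might take the section 6 schedule as further evidence, since it appears to mark the last call at week 57 and none at week 60. Clinic and FVC marks at weeks 8, 20, 32, 44 and 52 each sit one column left of a 12-weekly pattern, so cells may have shifted in conversion to text. The point does not rest on that table.

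**Conclusion.** The point holds in a limited form. As plainly read, section 11.2.1 shortens the all-event reporting window for a subject who leaves the study within 28 days of the last dose, and it conflicts with the post-dose call required in section 6, the synopsis and the Protocol Amendment. The loss is 28 − D days per affected subject: all 28 for a same-day exit, 14 for an exit on day 14, none from day 28 onward. The number of subjects affected cannot be derived from the documents.

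The consequence is incomplete event counts, grades, outcomes and listings for early leavers, including possible omission of unattributed SAEs and deaths. The primary tolerability count is not biased by it. The conclusion rests on reading A and on drug not being given after study exit. If reading B was intended, no days are lost, but the sentence still needs rewording so that it cannot be applied the other way. It should be corrected because safety is what this pilot is meant to establish and the repair is small.

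**What to change.** Replace the end-of-period wording in section 11.2.1 with a rule tied to the last dose only: all AEs and SAEs are reported through 28 days after the last administration of study treatment, regardless of study status, unless the subject withdraws consent to further contact. The consent exception is needed because the Withdrawal section allows exit at the patient's request. Leave in place the existing rule for attributed SAEs after the window.

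Because section 11.3.2.2 defines reportable deaths by the same period, it is corrected by the same change. The cost is one reworded sentence, submitted to the IRB as an amendment under section 10.1, and at most one call per early leaver, which section 6 already requires.
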